### **5.2.3 Mean Duration of Grade $\geq 2$ Radiation Dermatitis Using the CTCAE Criteria**

The total duration is defined as the spanning from first onset date with CTCAE grade  $\geq 2$  to last resolved date (i.e., next dermatitis assessment date after the last grade  $\geq 2$ ). Descriptive statistics by treatment groups will be summarized for the total duration, overall and by subgroups of interest for the subset of patients with at least one CTCAE grade  $\geq 2$ . In addition to the descriptive analyses, the mean duration across 3 treatment groups will be compared using an ANCOVA model in a similar manner to the analysis in Session 5.2.1.

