##### **3.2.1 Intent-to-treat Population (ITT)**

The intent-to-treat (ITT) population includes all randomized patients whether or not they received study drug. Patients will be summarized according to the treatment to which they were randomized.

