#### **4.3 Study Drug Exposure**

Study treatment exposure (i.e. RTA 408 Lotion 0.5%, RTA 408 Lotion 3%, or vehicle lotion), including treatment duration will be summarized by treatment group with descriptive statistics. Similarly, the incremental and cumulative radiation exposure will be summarized by treatment group. The number of patients with interruptions in radiation treatment due to radiation tolerability will be tabulated overall and by study visit. Total study treatment exposure for each patient is calculated as follows: (last date of study treatment) – (first date of study treatment) + 1. Additionally, treatment compliance will be summarized, and the number of treatment compliant patients (i.e.,  $\geq 75\%$  compliant with dosing) will be tabulated. Compliance is calculated as [(total exposure days) – (total missed doses)] / (total exposure days).

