### 5.2 Secondary Efficacy

The following secondary efficacy endpoints will be analyzed for all randomized patients (i.e., ITT population). Interpretations of significance levels (i.e. P-values) will be done with caution since there is no formal control of type I error for multiple comparisons on the secondary efficacy endpoints.

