#### 5.2.1 Mean Maximum Radiation Dermatitis Grade of RTA 408 Lotion Compared to Administration of Vehicle

The first secondary efficacy endpoint is the mean maximum dermatitis grade. A maximum CTCAE grade per patient evaluated at weekly visits during the study will be identified.

Descriptive statistics will be summarized for the maximum dermatitis grade overall and by each of the subgroups of interest, breaking down by the 3 treatment groups.

An analysis of Covariance (ANCOVA) model will be conducted to compare the mean maximum dermatitis grade among the RTA408 0.5%, RTA408 3% and vehicle groups, adjusted for site, smoking status, breast cancer treatment prior to radiation therapy and total duration (in weeks) of study drug use. Pairwise RTA 408 lotion group comparisons with vehicle group will be estimated using the difference in adjusted means (and 95% confidence intervals, CI) from the ANCOVA model.

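### SAP 5.2.3 gives no duration to patients who never reach grade 2, so its ANCOVA, taken literally, compares affected patients only; a lesser point is the adjustment for observed weeks of study drug

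*SAP*

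**What the plan says.** On the population, SAP 5.2 states: "The following secondary efficacy endpoints will be analyzed for all randomized patients (i.e., ITT population"). SAP 3.2.1 defines that population broadly: "The intent-to-treat (ITT) population includes all randomized patients whether or not they received study drug".

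On the endpoint, SAP 5.2.3 states: "The total duration is defined as the spanning from first onset date with CTCAE grade" 2 or higher. The end point is the "last resolved date (i.e., next dermatitis assessment date after the last grade" of 2 or higher). The descriptive summaries are limited to patients with at least one such grade. The section then adds that "the mean duration across 3 treatment groups will be compared using an ANCOVA model in a similar manner to the analysis in Session 5.2.1". It names no population for that model and gives no value for a patient without an onset.

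On covariates, the model in SAP 5.2.1 is "adjusted for site, smoking status, breast cancer treatment prior to radiation therapy and total duration (in weeks) of study drug use". SAP 4.3 computes exposure from observed dates: "Total study treatment exposure for each patient is calculated as follows: (last date of study treatment") minus the first such date, plus 1.

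On missing data, SAP 3.6 fills missing efficacy endpoints with each patient's worst observation and plans a sensitivity analysis without imputation.

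**The concern.** An ANCOVA can use only patients who have an outcome value. If never-affected patients have none, the model compares women on drug who developed grade 2 or higher with women on vehicle who did. The secondary objectives count a maximum grade below 2 as treatment success, so this conditions on treatment failure. Randomisation does not protect such a comparison, and every case that the lotion prevents disappears from it. One programmer could drop these patients and another could code 0, and both could say that they followed the plan.

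A patient whose last assessment still shows grade 2 or higher has no later assessment to close her duration, and no rule covers her.

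Separately, weeks of study drug are known only after randomisation, and dermatitis can change them in either direction. Protocol 5.2 says that dermatitis can force changes to the radiation course, and Protocol 7.1 lets radiation delays extend drug use to at most 13 weeks. The SAP expects breaks of this kind: "The number of patients with interruptions in radiation treatment due to radiation tolerability will be tabulated overall and by study visit". In the other direction, SAP 1.2.2 allows study drug to stop for an adverse event, and Protocol 8.4.1 leaves continuation after grade 3 or higher skin toxicity to the investigator. Adjusting for a quantity that the outcome may influence can distort the treatment comparison.

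**Working it through.** **1. Does any rule supply the missing value?** The 5.2.3 definition needs an onset date, and a never-affected patient has none. Under 3.6, filling her missed weekly grades with her worst grade gives 0 or 1, which creates no onset. If the rule is applied to duration itself, she has no observed duration to carry. SAP 5.2 names the population but assigns no value.

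**2. Effect on the estimate.** Let p be the proportion of vehicle patients affected, d the proportion of patients in whom the drug prevents grade 2, m the mean duration among affected vehicle patients, and mp the mean duration that the prevented cases would have had. Remaining cases are taken as unchanged.

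- Affected-only difference: (p·m − d·mp)/(p − d) − m = d(m − mp)/(p − d). This is 0 when mp = m, whatever the incidence.
- Difference over all randomised, with 0 days for never-affected: −d·mp.

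**3. Numbers.** The 59 per arm is from Protocol 7.2. The documents supplied give no incidence or duration, so the rest is assumed: m = mp = 21 days.

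| Affected, vehicle / drug | Expected patients with a value | Mean days over all | Difference, all | Difference, affected only |
|---|---|---|---|---|
| 90% / 70% | 53.1 / 41.3 | 18.9 / 14.7 | −4.2 | 0 |
| 80% / 60% | 47.2 / 35.4 | 16.8 / 12.6 | −4.2 | 0 |
| 60% / 40% | 35.4 / 23.6 | 12.6 / 8.4 | −4.2 | 0 |
| 80% / 80% | 47.2 / 47.2 | 16.8 / 16.8 | 0 | 0 |

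With m = mp = 28 days and d = 0.20 the all-randomised difference is −0.20 × 28 = −5.6 days. With d = 0.10 it is −2.8 days.

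**4. Illustrative power** (one active arm against vehicle, two-sided 5% t test without covariates).

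- Mean 21 days, SD 12, durations limited to 7–70 days, d = 0.20, 4,000 simulated trials per row of the table. The affected-only test favours the drug in 2–3% of trials, which is chance level. The all-randomised test does so in 42–46%.
- Mean 28 days, SD 12–20, d = 0.20, 60–90% of vehicle patients affected. The affected-only test rejects in about 5%, and the all-randomised test in 30–51%. With d = 0.10 the latter has 11–17%.

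**5. Covariate: how far can it move?** Protocol 8.1 allows 45–50.4 Gy at 1.8 Gy (25–28 fractions) or 46–50 Gy at 2 Gy (23–25), plus a 10–16 Gy boost. Assuming 2 Gy boost fractions (5–8) and five fractions a week, the plan is 28–36 fractions, or 5.6–7.2 weeks. Adding 1 week before and 2 after gives 8.6–10.2 weeks. The 13-week limit leaves 2.8–4.4 weeks, but part of this is delayed radiation starts (run-in of up to 14 days), which precede any dermatitis.

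Illustrations for the maximum-grade analysis, all on assumed inputs:

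- Breaks of 1–2 weeks in 10–50% of grade 3 or higher patients, with no early stopping, shrink an effect of about half a grade by 0.5–17%.
- Early stopping in 30% of those patients, with no breaks, shrinks it by 8%.
- With 30% early stopping and 30–50% breaks together, the shrinkage is about 0–1.3%, because the two move drug weeks in opposite directions.

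**The case against.** The best defence is that 5.2.3 restricts only its descriptive sentence to affected patients. The ANCOVA comes as an addition, SAP 5.2 requires all randomised patients, and the objective in SAP 1.1.2 has no affected-only limit. Read together, coding 0 days is a natural inference. That is fair: this is an omission, not a declared choice. It does not close the gap, because the definition and the population statement cannot both be carried out without a rule that nobody has written.

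The consequence is also limited. SAP 5.2 tells the reader to treat secondary p-values with caution, prevention is reported through maximum grade below 2 in 5.2.2, and the primary longitudinal model does not use this endpoint. All of that stands.

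On the covariate, breaks and early stopping act in opposite directions and part of the spare time precedes dermatitis, so the upper shrinkage figure needs breaks alone. That stands too. A never-dosed patient has no dates for the 4.3 formula, but 0 weeks is an obvious reading and I do not press it.

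A reader might infer that the affected-only comparison would make the drug look harmful. By the formula in step 2 this happens only if the prevented cases would have been shorter than average. With p = 0.80, d = 0.20, m = 21 and mp = 10.5 it gives 0.20 × 10.5 / 0.60 = +3.5 days, while the all-randomised difference is −2.1. Simulating prevention of only the shortest cases gives +3.8 to +5.7 days affected-only. The documents contain nothing on which cases would be prevented, so a reversal is a possibility and not a finding.

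**Conclusion.** The point holds as a gap in the specification of a secondary endpoint, and it should be fixed. As written, the duration ANCOVA can use only affected patients, contrary to the stated population, and it has no end date for unresolved cases. The structural result needs no assumed incidence: if prevented cases are of average length and remaining cases are unchanged, the affected-only difference is 0. The sizes (4.2 or 5.6 days over all randomised, and all power figures) rest on assumed incidence, duration and spread, and are illustrative only.

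The weeks-of-drug covariate is a lesser fault. It is measured after randomisation and can be lengthened or shortened by dermatitis. The direction and size of its bias cannot be determined from the documents and may be negligible, so they do not support a claim of material shrinkage. Nor do they support any inference that the primary test is compromised.

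**What to change.** Change the SAP before database lock.

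(a) In 5.2.1, and so in 5.2.3, delete the term for weeks of study drug use. Keep site, smoking status and breast cancer treatment.

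(b) In 5.2.3, compare duration in all randomised patients, with 0 days if grade 2 or higher never occurs. Keep 3.6 worst-observation imputation for missed scheduled visits as the main rule, so that a patient who leaves with active grade 2 or higher is counted through the last scheduled visit. Ending her duration at the last attended visit would reward leaving. A patient with onset at the second post-radiation week who resolves at follow-up four weeks later scores 28 days, while the same patient lost after onset would score 1. If grade 2 or higher is still present at the final visit, end the duration on that date, counted inclusively so that no affected patient scores 0. Run the no-imputation analysis as the sensitivity analysis that 3.6 already plans.

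(c) Report by arm the number unresolved and the number who left without grade 2 or higher, and repeat the analysis without the latter.

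(d) Label the affected-only summary as descriptive. A rank test stratified by the two randomisation factors is optional as a sensitivity analysis for the many zeros.

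The cost is wording and a few extra tables; no new data are needed. There are two drawbacks. Early leavers without grade 2 or higher score 0, which the repeat analysis in (c) addresses. Worst-observation imputation also lengthens the duration of a patient whose dermatitis had resolved before a missed visit, which the no-imputation analysis will show.

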6.2. Secondary Study Objectives

The secondary objectives of this study are the following:

1. To determine the mean maximum radiation dermatitis grade measured with CTCAE of RTA 408 Lotion (0.5% and 3%) compared to administration of vehicle
2. To determine the proportion of patients with treatment success, defined as post-baseline maximum dermatitis grade < 2 using the CTCAE criteria following administration of RTA 408 Lotion compared to administration of vehicle
3. To determine the mean duration of grade ≥ 2 radiation dermatitis using the CTCAE criteria following administration of RTA 408 Lotion compared to administration of vehicle
4. To determine the extent of systemic exposure to RTA 408 following administration of RTA 408 Lotion following radiation therapy
5. To evaluate patient-reported outcomes (Skindex-16)

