^b Visit 2 (7 days prior to radiation treatment) is the day of randomization and application of the first dose, and must occur at least 5 and no more than 9 days prior to the first day of radiation treatment. If the start of radiation treatment is delayed, patients should continue administering study drug twice daily until the first dose of radiation up to a maximum of 14 days. If the time from randomization to first dose of radiation exceeds 14 days, the medical monitor should be contacted to decide on an appropriate action. Patients may be randomized after meeting the inclusion / exclusion criteria and before study drug lotion is first administered as long as patients apply study drug lotion for at least 5 days prior to the first day of radiation treatment. Patients with either morning or afternoon randomizations may apply lotion in the clinic and again before bedtime for two doses on that day.

^c Visit 3 should occur on the day of the first radiation treatment. If radiation treatment is in the morning, the radiation treatment will be the third to last procedure (radiation treatment > study drug application > PK). If radiation treatment is in the afternoon, radiation treatment will be the second to last procedure, and the last procedure will be PK, as study drug will have been applied at least 4 hours prior to radiation treatment.

^d Study visits during radiation treatment therapy must occur weekly beginning with Day 1 of radiation treatment.

^e At the end of radiation treatment, patients must complete Visit 9 assessments. Visit 9 must be the last day of the 10 – 16 Gy boost. Visit 8 is needed for patients who require radiation therapy for 6 weeks. If radiation therapy is extended longer than 6 weeks, then assessments at Visit 8 should be repeated weekly until the end of radiation visit (Visit 9). A weekly study visit should not be performed if the visit falls 1 or 2 days prior to the last day of radiation (Visit 9), or 1-2 days after the last day of radiation.

^f Visit 10 should occur approximately 1 week (7 calendar days) after the completion of radiation therapy (Visit 9).

^g Visit 11 should occur approximately 1 week (7 calendar days) after Visit 10 (*i.e.*, 2 weeks after the completion of radiation therapy).

^h Follow-up visit will occur approximately 4 weeks after the final study drug application. These procedures should be performed at the end of study and for early termination.

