9.2.2. Permitted Medications

Prophylactic anti-emetics will be allowed, at the discretion of the treating physician, after the patient has experienced \geq CTCAE grade 1 nausea or vomiting.

Other allowed concomitant medications include:

- Antibiotics;
- Vitamins or minerals;
- Pain medication as authorized by the treating physician;
- Other medications intended to manage concurrent diseases, as authorized by the treating physician;
- Hormonal antagonists (including tamoxifen, aromatase inhibitors and/or herceptin);
- Any required immunizations and/or vaccinations;
- Oral, implantable or injectable contraceptives.

Patients may take ibuprofen, aspirin and/or over-the-counter cough / cold medications, but these concomitant medications must be recorded. Patients taking medication chronically should be maintained on those same doses and dose schedules throughout the study period, as medically feasible.

If patients develop Grade 2 or higher radiation dermatitis and the radiation dermatitis is believed to be inadequately controlled in the opinion of the Investigator, additional topical creams, lotions, hydrocortisone or other escape medications may be prescribed and then must be documented in the CRF. Patients should apply escape medications 1-3 hours after study drug application. Any residual escape medication should be removed prior to study drug application. However, in patients with radiation dermatitis < Grade 2, no concomitant medications may be prescribed or administered to prophylactically prevent the incidence of Grade 2 or higher radiation dermatitis.

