Following randomization, patients will be assessed in person at weekly visits during administration of study treatment. A follow-up visit will occur 4 weeks after last application of RTA 408 Lotion or vehicle. Due to the variation in radiation treatment schedules, exact study days or procedures may be shifted to fall within a window of 2 days based on radiation treatment schedules. However, all enrolled patients must continue to apply RTA 408 Lotion for two weeks after the completion of radiation. If a radiation therapy treatment break is extended beyond 5 days, the medical monitor should be consulted to determine if application of study drug should continue.

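### The duration of grade ≥2 dermatitis is one first-to-last span, so time graded 0 or 1 between two episodes counts as time at grade ≥2

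*SAP*

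**What the plan says.** The secondary objective in Protocol 6.2, repeated in SAP 1.1.2, is "To determine the mean duration of grade ≥ 2 radiation dermatitis using the CTCAE criteria following administration of RTA 408 Lotion" against vehicle. The protocol does not define how duration is computed.

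SAP 5.2.3 supplies the rule: "The total duration is defined as the spanning from first onset date with CTCAE grade" 2 or more, "to last resolved date (i.e., next dermatitis assessment date after the last grade" at that level. Descriptive summaries are given "for the subset of patients with at least one CTCAE grade" of 2 or more, and the three groups are compared by ANCOVA. There is no rule for separate episodes and no sensitivity analysis with another definition.

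On timing, SAP 1.2 states that "patients will be assessed in person at weekly visits during administration of study treatment". The footnotes to Protocol 7.5 add that the "Follow-up visit will occur approximately 4 weeks after the final study drug application".

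**The concern.** The objective asks how long patients are at grade ≥2. The SAP rule measures the time from first onset to final resolution. The two agree only if each affected patient has one unbroken run of readings at grade ≥2, and the SAP does not state that assumption.

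Several features of the design allow the run to break:

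- Grades are read weekly by local site staff (SAP 1.2 and 2.2.2), so one borderline reading of 1 versus 2 can open or extend the span.
- From grade 2 on, if control is judged inadequate, "additional topical creams, lotions, hydrocortisone or other escape medications may be prescribed and then must be documented in the CRF" (Protocol 9.2.2). A grade can therefore fall while radiation continues.
- Radiation interruptions are foreseen (Protocol 7.1, SAP 1.2).
- SAP 3.6 replaces missing efficacy data with the patient's worst observation. If this is done visit by visit, a missed late visit can create a second episode that was never observed.

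At stake is the interpretation of the between-arm comparison. Time spent below grade 2 between episodes earns no credit, and one isolated reading can change a patient's value by weeks.

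**Working it through.** The documents give no figure for this endpoint, so there is none to reproduce. The check applies the SAP rule and an interval-sum rule to the same grade sequences.

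**Definitions.** Let t(i) be the assessment dates and g(i) the grades. Let f and l index the first and last readings at grade ≥2.

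- Span (SAP 5.2.3) = t(l+1) − t(f).
- Sum = total of t(i+1) − t(i) over every i with g(i) ≥ 2.
- Excess = span − sum = total of t(i+1) − t(i) over i between f and l with g(i) < 2.

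The excess is never negative, and the closing interval cancels out of it.

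**Assumed schedule**, counted from the first radiation day: Visits 3 to 8 on days 0, 7, 14, 21, 28 and 35; Visit 9 on day 42; Visit 11 on day 56; Visit 12 on day 84. The schedule table appears to have no dermatitis reading at Visit 10. Because the table layout is uncertain, results are also shown with a reading below 2 on day 49.

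**Worked case.** Grade 2 at Visit 5 (day 14) and Visit 9 (day 42) only. Three readings, at Visits 6, 7 and 8, lie between them.

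- Span: 56 − 14 = 42 days without Visit 10; 49 − 14 = 35 days with it.
- Sum: 7 + 14 = 21 days without Visit 10; 7 + 7 = 14 days with it.
- Excess: 21 days either way, which is 50% or 60% of the span.

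**Other illustrative patterns** (without / with a Visit 10 reading):

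| Visits at grade ≥2 | Span, days | Sum, days | Excess, days |
|---|---|---|---|
| 6 to 9, unbroken | 35 / 28 | 35 / 28 | 0 |
| 5, then 7 to 9 | 42 / 35 | 35 / 28 | 7 |
| 5 and 11 | 70 / 70 | 35 / 35 | 35 |
| 4 and 11 | 77 / 77 | 35 / 35 | 42 |

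**Imputation.** Suppose grade 2 occurs at Visit 6 (day 21) only: both rules give 28 − 21 = 7 days. If Visit 11 is missing and is imputed as grade 2, the span becomes 84 − 21 = 63 days and the sum 7 + 28 = 35 days. Both are inflated by the imputation, the span by more.

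**Group means.** The documents give no recurrence rate, so this step rests on assumptions: severity rises to a peak near radiation day 47 and then heals, and weekly readings carry an error SD of 0.3 to 0.5 grade. Simulations on that basis put a gap in 10 to 34% of affected patients. The excess was 8 to 12 days in those patients and about 1 to 3.5 days averaged over all affected patients. In one such simulation the between-patient SD was 17.5 days (span) against 17.2 (sum) at error SD 0.3, and 18.8 against 17.6 at 0.5. With no reading error the rules agreed.

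**The case against.** The protocol leaves duration undefined and the SAP governs. Time from first onset to final resolution is an explicit and reproducible meaning of the word. This stands as far as it goes: the SAP does not contradict a protocol rule. But the objective names the duration of grade ≥2, and a span that includes lower grades needs a different label.

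The interval sum is not the truth either. In the smooth-healing model a gap arises only from misreading, and 65 to 84% of the gap days were truly at grade ≥2. A reader might infer that the counted days are days of healed skin; they are only days graded below 2. Both rules overshot the true time over all affected patients, the span by 13 to 15 days and the sum by 11 to 12. Most of that bias comes from weekly reading and the closing interval, and it survives the change. The sum was still the closer of the two in patients with gaps.

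A reader might also infer that a real benefit would be hidden. The simulations do not show this. For an assumed lotion that heals faster or lowers the peak, mean differences were nearly equal (6.6 against 6.5 days; 11.6 against 11.5), and the standardized effect under the span was 0 to 11% lower. A near-total loss would need a treatment that only interrupts episodes. The documents do not suggest one, and that case was not simulated.

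Finally, grades between episodes are used elsewhere: in the primary mixed model (SAP 5.1) and in the by-visit logistic model (SAP 5.2.2). Duration is one secondary endpoint without type I error control (SAP 5.2).

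**Conclusion.** The point holds. As written, the rule counts time graded 0 or 1 between episodes as time at grade ≥2. The excess is 21 days in the worked case, 7 to 42 days across the interrupted patterns tried, and zero for a single unbroken episode. These figures assume nominal visit days and invented grade sequences.

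It would be tempting to say that recurrent episodes are to be expected in this trial. The documents permit them but neither predict them nor give a frequency. The effect on group means is therefore unknown, and the 1 to 3.5 days above depends on the assumed severity curve and reading error. The expected loss of precision is small. This is a worthwhile correction to a secondary endpoint before database lock, and it does not threaten the primary analysis.

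**What to change.** In SAP 5.2.3, define total duration as the sum of days in intervals between consecutive dermatitis assessments that begin with grade ≥2. Keep the first-to-last span as a supplementary summary labelled *time from first onset to final resolution*. The set of affected patients and the ANCOVA stay the same, because both rules select the same patients.

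The cost is one sentence and a small programming change, with no new data. Mean durations become slightly shorter, and a single falsely low reading within an episode removes one interval, nominally 7 days during radiation. The change does not settle how to close the duration of a patient still at grade ≥2 at the last assessment, or whether imputation under SAP 3.6 works by visit. Those are separate matters that affect both rules.

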### 2.2 Endpoint Measures

#### 2.2.1 Efficacy Endpoints

The primary efficacy endpoint is dermatitis grade (CTCAE v4.03).

The secondary efficacy endpoints are mean maximal dermatitis grade, proportion of patients with maximal dermatitis grade < 2, duration of CTCAE grade  $\geq 2$ , proportion of patients who develop moderate erythema, the proportion of patients who develop dry desquamation and the proportion of patients who develop moist desquamation.

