### **3.6 Missing Data**

Missing data will not be imputed for safety endpoints. Missing efficacy endpoints will be imputed using the worst-observation reported for each patient. Sensitivity analyses for efficacy endpoints will be performed with no imputation for missing data. Additional sensitivity analyses may be considered as needed.

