#### **3.7.3 Unscheduled Visits**

The CRF nominal study visits will be used for all safety analyses. Unscheduled visits will be reflected in summarization of changes to worst post-baseline measures.

Additionally, for missing scheduled assessments with an unscheduled assessment available after the previous scheduled visit but before the next scheduled visit, the closest unscheduled assessment will be used in the place of missing scheduled efficacy assessments

All unscheduled visits will be listed.

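### Duration of grade ≥2 dermatitis has no defined end for a patient still unhealed at her last assessment, and worst-grade imputation, if applied first, can remove or stretch the duration of others

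*SAP*

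**What the plan says.** - **Definition.** SAP 5.2.3 runs the duration from the first date with grade ≥2 to the "last resolved date (i.e., next dermatitis assessment date after the last grade" ≥2.
- **Patients and analysis.** The summary is "for the subset of patients with at least one CTCAE grade" ≥2, and "the mean duration across 3 treatment groups will be compared using an ANCOVA model" built like the one in SAP 5.2.1.
- **Missing data.** SAP 3.6: "Missing efficacy endpoints will be imputed using the worst-observation reported for each patient". It adds: "Sensitivity analyses for efficacy endpoints will be performed with no imputation for missing data".
- **What counts as an endpoint.** SAP 2.2.1: "The primary efficacy endpoint is dermatitis grade (CTCAE v4.03"). Duration of grade ≥2 is listed there separately, as a secondary endpoint.
- **Substitution.** Under SAP 3.7.3 "the closest unscheduled assessment will be used in the place of missing scheduled efficacy assessments", provided it falls "after the previous scheduled visit but before the next scheduled visit".
- **Last assessment.** In Protocol Table 3 and SAP Appendix 1, Visit 12 (post-radiation week 6, also the early-termination visit) is the last scheduled dermatitis assessment. The one before it is Visit 11 (post-radiation week 2).
- **Unresolved events.** The only SAP rule for an open event is in 7.1.1. It covers adverse events and calculates no duration for them. Nothing comparable is given for dermatitis.

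**The concern.** The end date exists only if an assessment follows the last grade ≥2. A patient who is still at grade ≥2 at Visit 12, at early termination, or at an earlier visit with none after it has no end date. She is in the set to be summarised but has no value to summarise. If the programmer leaves her out, as the adverse-event convention would suggest, the loss depends on the outcome. Someone unhealed six weeks after radiation generally has one of the longest reactions, so the arm mean is pulled down. How far depends on how many such patients each arm has.

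The second issue is the order of two steps. If missing visit grades are first filled with the patient's own worst grade, a missed Visit 12 becomes grade ≥2 for anyone who was ever affected. A recovery seen at Visit 11 is then re-opened with nothing after it. Filled grades at other visits can move the onset earlier or the end later.

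Mean duration is a named secondary objective, and SAP 1 makes the SAP govern over the protocol. If the SAP is silent, the rule will be set in programming.

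**Working it through.** **The plan's own figure.** There is none for duration. Protocol 13.1 and SAP 1.3 show no text, so no effect size or SD is available. The only size figure is 3 × 59 = 177, which agrees with Protocol 7.2.

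**Step 1: does another rule supply the missing end date?** SAP 3.6 does not. Applied to visit grades, it adds only grades ≥2 for an affected patient. Applied to duration itself, it has nothing to carry, because each patient has at most one duration. SAP 3.7.3 replaces a missed assessment; it does not add one after the last.

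**Step 2: apply the rule to visit patterns.** Days are counted from the first radiation day as day 1. Visits 3–8 fall on days 1, 8, 15, 22, 29 and 36, and Visit 9 on day 43 (six weeks of radiation assumed). Visit 11 is day 57 and Visit 12 day 85. Table 3 as printed has no dermatitis mark at Visit 10; the argument does not depend on that. Duration = (first assessment after the last grade ≥2) − (first grade ≥2). First grade ≥2 is on day 29 throughout.

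| Pattern | Observed grades only | Fill first |
|---|---|---|
| Last ≥2 at Visit 9; below 2 at Visits 11 and 12 | 57 − 29 = 28 | 28 |
| Still ≥2 at Visit 12 | none (at least 85 − 29 = 56) | none |
| ≥2 at Visit 11, Visit 12 missed | none (at least 57 − 29 = 28) | none |
| Below 2 at Visit 11, Visit 12 missed | 28 | none (≥2 carried to day 85) |
| As above, unscheduled grade below 2 used for Visit 12 | 28 | 28 |
| As first row, but Visit 5 missed before onset | 28 | 57 − 15 = 42 |
| Below 2 at Visit 9, Visit 11 missed, below 2 at Visit 12 | 43 − 29 = 14 | 85 − 29 = 56 |

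Rows 2 and 3 have no duration with or without the fill. Row 4 loses its duration only because of the fill.

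**Step 3: how many patients?** All inputs except 59 per arm are assumptions. In a simulation, 75% are affected, onset is normal (mean day 33, SD 6), and true duration is gamma with shape 2 and mean 25 days. Visits fall on days 0, 7, …, 35, 44, 58 and 86, counting the first radiation day as 0. About 42 patients per arm have an observed grade ≥2.

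| Visit 12 missed | No duration, no fill | No duration, fill first | Added by fill |
|---|---|---|---|
| 0% | 3.6 | 3.6 | 0 |
| 5% | 4.3 | 5.5 | 1.2 |
| 10% | 5.1 | 7.4 | 2.3 |

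The first entry is sensitive to the gamma shape: shapes 1 to 6 move it from 5.4 to 0.8.

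A cruder formula shows the range. Let *a* be the share affected, *u* the share unhealed at the last attended visit (held fixed) and *m* the share missing Visit 12, independent of *u*. The count is 59·a·u without the fill and 59·a·[1 − (1 − m)(1 − u)] with it. For a = 60%, m = 10%, u = 5%: 35.4 × 0.05 = 1.8, against 35.4 × 0.145 = 5.1. Over a = 40–80%, m = 5–20% and u = 2–10%, the counts are 0.5–4.7 and 1.6–13.2 per arm.

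**Step 4: effect on the arm difference if unhealed patients are left out.** Removing a share *u* with span *L* from an arm with mean *μ* leaves (μ − uL)/(1 − u). Assume means of 30 (vehicle) and 25 (active), so a true difference of 5.0 days, and L = 60.

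- 10% vehicle, 4% active: 24/0.90 − 22.6/0.96 = 26.67 − 23.54 = 3.1.
- 6% and 3%: 26.4/0.94 − 23.2/0.97 = 28.09 − 23.92 = 4.2.
- 4% and 10%: 27.6/0.96 − 19/0.90 = 28.75 − 21.11 = 7.6.
- Equal rates: 5/(1 − u), so 5.1, 5.3 and 5.6 at 2%, 6% and 10%.

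With onset on day 33 and Visit 12 on day 86, L = 53. The first and third cases then give 3.6 and 7.2.

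**The case against.** The strongest reply is that the plan is silent and does not exclude anyone. SAP 5.2.3 summarises everyone with a grade ≥2, which includes the unhealed. That is correct: a reader might infer that the SAP drops these patients, and no section says so. What stands is that the rule as written gives them no value and an ANCOVA needs one, so someone must either leave them out or invent a rule.

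On imputation, a reader might infer that every affected patient who misses Visit 12 loses her duration. The documents do not support that, for four reasons.

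- The order of imputation and derivation is not stated. SAP 5.2.3 works on assessment dates, and SAP 3.6 creates no date for a missed visit. Filling first is the natural reading because grade is itself the primary endpoint, but it remains a reading.
- An unscheduled assessment may stand in under SAP 3.7.3, although that wording requires a next scheduled visit and Visit 12 has none.
- Early terminators should have the Visit 12 procedures, and patients who only stop study drug are asked to attend all visits.
- The no-imputation sensitivity analysis keeps the 28 days in row 4.

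Nor should the fill be charged with all the losses at a missed Visit 12. Patients still at grade ≥2 at Visit 11 have no end date either way.

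The bias figures need unequal unhealed rates, which nothing in the documents suggests; with equal rates the distortion is small. The endpoint is also secondary, and SAP 5.2 says its p-values are to be read with caution. Both points stand. They limit the weight of the finding but do not fill the gap.

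**Conclusion.** The point holds in two parts of different strength. First, and without condition, duration is undefined for a patient whose last assessment shows grade ≥2, and no section supplies an end date or a censoring rule. The no-imputation analysis does not help, because nothing is missing for her. Second, and only if SAP 3.6 is applied to visit grades before duration is derived, an affected patient with no Visit 12 grade and no unscheduled substitute loses her end date even if already seen below grade 2, and other missed visits can lengthen defined durations. The no-imputation analysis removes this part.

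The size cannot be known from the documents. Under the simulation's assumptions, about 3.6 of some 42 affected patients per arm have no duration with complete Visit 12 attendance. At 5–10% missed, 4.3–5.1 have none without the fill, and the fill adds 1.2–2.3.

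A reader might infer a known bias for or against the drug. The documents do not support that. The direction depends on which arm has more unhealed patients, and the figures of 3.1 to 7.6 days against a true 5.0 only illustrate the range. The primary analysis is not affected by this gap. The SAP should be changed, but this is not a critical flaw.

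**What to change.** Amend SAP 5.2.3 before database lock:

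- (a) Derive onset and resolution from observed assessments only, and state that the SAP 3.6 fill does not apply to duration.
- (b) Keep every patient whose last observed grade is ≥2 and treat her duration as right-censored at that assessment.
- (c) Compare arms with a method that handles censoring, such as restricted mean duration to a fixed, pre-specified horizon. If ANCOVA is kept, report it with duration counted to the last assessment and, as a sensitivity analysis, to the planned Visit 12 date. The second should not be the main analysis: for a patient who terminated early it is itself a worst-case fill.
- (d) Report the number censored per arm.

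The cost is a few sentences and one flag in the derived dataset, with no new data. The small downside is that the result depends on the chosen horizon, so the horizon has to be fixed in advance.
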